#### **4. ETHICAL ISSUES**

This study will be conducted in compliance with the principles outlined in the World Medical Association's Declaration of Helsinki (**see Appendix 5**).

##### **4.1 Institutional Ethics Committee Approval**

Each participating centre must obtain written approval(s) from their Hospital Research Ethics Committee (e.g. Institutional Review Board [IRB]), and other regional or national regulatory bodies before patient recruitment can commence. Any protocol amendments, serious adverse event (SAE) reports and routine reporting to the IRB will be the responsibility of the Principal Investigator (PI) at each participating centre.

##### **4.2 Consent**

The majority of patients admitted with AIS require emergency care. Some aspects of this care are thrombolytic treatment with rtPA and management of hypertension which needs to be treated urgently. However, the nature of this acute condition means that the patient may be too unwell to comprehend the information that must be given in the consent process and this consent needs to be obtained swiftly to avoid delays in urgent treatment. The optional consent

procedures for this study are detailed below and should be followed according to local IRB guidelines.

### Patient Consent

Wherever possible, the patient will be approached to directly give written informed consent. An information statement will be given to the patient and the implications for consenting to the study will be explained by a clinician familiar with the study protocol.

### Person Responsible Consent

If the patient is not fully competent to give informed consent, for example because of a reduced level of consciousness or confusion, the patient's 'person responsible' will be approached to provide informed consent on his or her behalf.

Under the Guardianship Act of 1987 in New South Wales, Australia, a 'person responsible' are the legally appointed guardian, their spouse or de-facto spouse or same sex partner, or if there is none, their unpaid carer, or if there is none, their relative or friend who has a close relationship with the person.

The patient will be made aware of this process as soon as they are well enough and have an opportunity to withdraw the consent. If willing to continue participation in the study, the patient will be asked to sign their own consent form.

If the patient is dying or is still unable to record their personal consent by the time of completed follow up on the study, the consent given by their person responsible will stand and trial data will be retained. The reason for not obtaining the patient's consent will be documented, dated and signed in the patient's file.

If a patient is discharged from hospital before it has been possible to gain personal consent, the PI will make attempts to inform the patient of the study and gain written consent. If this has been unsuccessful after a minimum of 3 documented occasions, the consent given by their person responsible will stand and the trial data will be retained. The reason for not obtaining the patient's consent will be documented, dated and signed in the patient's file.

### Guardianship tribunal consent

In the situation where a patient is unable to give consent and a 'person responsible' is not available or cannot be contacted, clinicians should seek guardianship tribunal approval before enrolling eligible patients in the study. The patient will be made aware of this process as soon as they are well enough and have an opportunity to withdraw the consent. If willing to continue participation in the study, the patient will be asked to sign their own consent form. If the patient is not fully competent to give informed consent, for example because of a reduced level of consciousness or confusion, the patient's 'person responsible' will be approached as soon as possible to provide informed consent on his or her behalf.

In the case of a patient's death, the PI should use discretion on a case by case basis before contacting the 'person responsible' in recognition of the potential distress that may exist as the result of a death. In either case, an explanation of the lack of patient or surrogate consent will be document in the patient's file.

### Delayed consent

The circumstances surrounding emergency care research are such that it may not always be possible to obtain consent from either the patient or next of kin without delaying the initiation of treatment, and therefore risk reducing any potential benefits to the patient. In the situation where a patient is unable to give consent and a next of kin or other person responsible is not available or cannot be contacted, clinicians may enrol eligible patients and inform the patient or their person responsible for the patient as soon as possible so that delayed consent can be requested. The reasons for being unable to obtain prior consent will be documented, dated and signed in the patient's file.

If the patient should die or continue to be unable to give informed consent at the end of the trial follow up period, the next of kin or person responsible should be approached to obtain delayed written consent. In the case of a patient's death, the PI should use discretion on a case by case basis before contacting the next of kin or surrogate, in recognition of the potential distress that may exist as the result of a death. In either case, an explanation of the lack of patient or person responsible consent will be document in the patient's file.

Delayed consent in a clinical trial of emergency care is considered by the World Medical Association in the Declaration of Helsinki. This document states:

*“Research on individuals from whom it is not possible to obtain consent, including proxy or advance consent, should be done only if the physical/mental condition that prevents obtaining informed consent is a necessary characteristic of the research population.”*

This study includes such potentially eligible patients.

The Australian NHMRC also gives guidance to human research ethics committees on this issue:

*“When the nature of the research procedure is such that conformity to the principle of consent is not feasible, and neither the individual nor the individual's representative can consider the proposal and give consent in advance, a Human Research Ethics Committee (HREC) may approve a research project without prior consent provided it is satisfied that:*

- (a) inclusion in the research project is not contrary to the interests of the patient; and*
- (b) the research is intended to be therapeutic and the research intervention poses no more of a risk than that which is inherent in the patient's condition and alternative methods of treatment; and*
- (c) the research is based on valid scientific hypotheses which support a reasonable possibility of benefit over standard care; and*
- (d) as soon as reasonably possible, the patient and/or the patient's relatives or legal representatives will be informed of the patient's inclusion in the research and of the option to withdraw from the research without any reduction in quality of care”.*

All four criteria apply to this study protocol including the uncertainty about the optimal rtPA dose and BP management in the medical profession and the current guidelines.

### Withdrawal of Consent

The information statement provided to the patient and/or the next of kin or surrogate will clearly state that the patient can be withdrawn from the study at any time without prejudice and explanation. Such withdrawal should be documented in the patient's file. If withdrawal of consent relates to the BP management alone, data collection can continue on documentation of this fact in the patient's files.

### **4.3 Confidentiality and privacy**

Every precaution should be taken to respect the privacy of patients in the conduct of the study. Only de-identified data will be submitted to the ICC at The George Institute for Global Health to maintain patient confidentiality. However, in the course of monitoring data quality and adherence to the study protocol the study monitor will refer to medical records at the participating hospital.

## **5. RANDOMISATION**

After confirmation of eligibility, patients are randomised via a central internet-based system at The George Institute, Sydney, Australia, either direct or via a specially developed Interactive Voice Randomisation System (in China). This will be done by connecting the study centre (e.g. emergency department or stroke unit) to the server at the ICC where the patient will be registered and the randomised treatments will be assigned for that particular patient.

The randomisation sequence will use a minimisation algorithm to ensure balance in key prognostic factors. Patients will be stratified according to:

1. site of recruitment
2. time from onset <3 hours versus ≥3 hours;
3. NIHSS score <10 versus ≥10;

From August 2015, the study allows patients only to be allocated to arm **[B]** 'level of BP control' only:

- intensive BP lowering to a target systolic BP range 130-140 mmHg within 60 minutes of Randomisation into the BP arm and to maintain this level for at least 72 hours (or until hospital discharge or death if this should occur earlier) or guideline-based BP lowering to a target systolic BP of <180 mmHg post-rtPA.

## **6. ALLOCATED STUDY TREATMENTS**

From August 2015, the attending clinician is required to consider their level of clinical uncertainty over the balance of potential benefits and risks pertaining to the level of BP control in each particular patient. Investigators are encouraged to adhere to study protocols, provide active care, but are free to modify a patient's treatment as required according to clinical judgment.

### **6.1 BP control arm**

#### *6.1.1 Early Intensive BP Lowering Group*

The aim is to achieve a systolic BP level 130-140 mmHg **within 60 minutes** of Randomisation into the BP arm *and* to maintain this BP level for the next 72 hours (or until hospital discharge or death if this should occur earlier). A standardised i.v. BP lowering regimen using locally available and approved i.v. BP lowering agents will be used, commenced in the emergency department and later in a high dependency area (e.g. acute stroke or neurointensive care unit) as is usual for patients receiving rtPA.

BP lowering will be titrated by repeat i.v. bolus or infusion, with a systolic BP of <130 mmHg being the safety threshold for cessation of therapy. It is anticipated that i.v. agents will be required for at least the first several hours in most cases but the timing of switch to oral BP lowering agents will be at the discretion of the responsible clinician according to BP control and patient status. It is also expected that i.v. therapy will continue to be required during the initiation of oral anti-hypertensive therapy, to maintain the systolic BP levels 130-140 mmHg.

When administering BP lowering treatment, care is required to ensure that severe hypotension is avoided in patients by checking first for potential dehydration and providing intravenous fluids.

Since the study seeks to address the impact of BP lowering and not a specific agent, and to ensure the trial result is maximally generalisable to existing routine practice, some flexibility is allowed in the use of locally available i.v. agents (e.g. urapidil, labetalol, hydralazine, metoprolol, clevidipine), but all other aspects treatment are standardised across sites. Patients on prior oral BP lowering agents should have this continued if possible and antihypertensive therapy prescribed when patients are clinically stable as per guidelines for secondary stroke prevention. Investigators are encouraged to adhere to study protocols, provide active care, but are free to modify a patient's treatment as required according to clinical judgment.

#### Intravenous treatment protocol

Intravenous treatment protocols, based on available medications, are provided in **Appendices 1A to 1H**. The intravenous treatment will be titrated against regular BP monitoring to achieve a target systolic BP range (130-140 mmHg) within 60 minutes. It is anticipated that intravenous control of systolic BP will be required for at least the first several hours.

#### Oral treatment protocol

The switch from intravenous to oral BP lowering treatment will be made at the discretion of the responsible physician, depending upon the control and stability of the BP and the clinical status of the patient. It is anticipated that oral treatment will be started by 24 hours. An oral treatment protocol is provided in **Appendices 1A to 1H**. Combination treatment with an ACE inhibitor and diuretic will be recommended on top of other therapy as the first line oral treatment on the basis of the results of the PROGRESS trial and established best practice for the long-term prevention of BP-related events in patients with cerebrovascular disease.

The oral treatment protocol will also include a defined strategy for titration of treatment to achieve effective early systolic BP control once oral treatment is commenced. If the patient is unable to swallow, treatment should be administered via nasogastric tube.

For the intervention group, the goal is to maintain systolic BP levels within (130-140 mmHg) for 72 hours of hospital stay. If the patient is transferred to another hospital facility within 72 hours, then attempts should be made to continue therapy to achieve the systolic BP target of (130-140mmHg). The target systolic BP after hospital discharge remains <140 mmHg, as per guideline-based recommendations for high risk vascular disease patients. BP levels will be reviewed at 28 days follow-up and medication adjusted as necessary to maintain systolic BP <140 mmHg.

#### *6.1.2 Control / Conservative BP Management Group*

Patients allocated to the control group will receive management of BP that is based on a standard guideline, as published by the AHA (refer to **table 3** in Background section). **Appendix 1I** outlines the protocol for Control patients. For this group, the attending clinician may consider commencing BP treatment if the systolic level is greater than **180 mmHg**, however and the first line treatment will be oral (including nasogastric if required) and/or transdermal routes or according to local regulatory approval if applicable. Should control of systolic BP not be achieved via these routes, i.v. treatment may be started until the target

systolic BP of 180 mmHg is achieved. The oral and i.v. agents used will be the same as in the intensive BP lowering group as detailed in **Appendices 1A to 1H**. Oral anti-hypertensive therapy may be started at any time the treating physician feels the patient is stable. Oral therapy must be started by Day 7. The target systolic BP after hospital discharge is <140 mmHg, as per guideline-based recommendations for high risk vascular disease patients.

## **6.2 Previous Use of Antihypertensive Therapy in Both Groups**

Patients who have been taking antihypertensive therapy prior to randomisation will have their usual medication continued when oral administration is possible, unless the agents are considered to be inappropriate by the responsible physician (e.g. poor compliance, intolerance, or adverse events). Otherwise, based on the results of the PROGRESS trial, a combination of an ACE inhibitor and diuretic should be added to any existing antihypertensive therapy when the patient is considered medically stable.

## **7. DISCONTINUATION OF ALLOCATED MANAGEMENT POLICY**

The investigator must not deviate from the protocol except the patient/surrogate chooses to withdraw consent to participation in the study. However, allocated management in either group should be discontinued or modified if any of the following occur:

- a. SAEs, which are in the opinion of the investigator, related to the trial protocol (refer to appropriate section for definitions).
- b. The investigator feels it is in the subject's best interest.

Follow-up data will be collected for all treated subjects except those who specifically withdraw consent for release of such information.

## **8. BACKGROUND CARE**

All patients will be managed in a facility with an adequate nurse/patient ratio and capacity for repeated neurological examination and non-invasive BP and heart rate monitoring (consistent recordings using automatic devices, every 15 minutes for 1 hour, then 6 hourly for 24 hours, then twice daily for 1 week). All BP measurements are from the non-paretic arm (or right arm in situations of coma or tetraparesis), with the patient resting supine for  $\geq 3$  minutes. All patients are to receive active care and best practice management according to guidelines, and neurointervention with intra-arterial thrombolysis and/or mechanical clot retrieval is still allowed according to local practice.

An acute stroke unit is defined as an area that:

1. is a geographically specific area where patients with acute stroke are managed;
2. has staff organised as part of a coordinated multidisciplinary team;
3. has staff who have special knowledge and skills in the management of acute stroke;
4. provides ongoing education about stroke management for staff, patients and caregivers;
5. has written protocols for assessment and management of common problems related to stroke.

During the study treatment and follow-up period, the usual management of acute stroke patients will be followed according to published guidelines (**see Appendix 4**) for the acute stroke care protocol. It is anticipated that background care may include significant use of treatments including drugs and endovascular intervention. Use of other therapies will be documented and compared between countries and should be balanced between randomised groups.

## 9. STUDY OUTCOMES

*Primary outcome for arm [A]* was the combined endpoint of death and disability as defined by the conventional dichotomised '0-1' versus '2-6' cut-point on the mRS at 3 months. *Primary outcome for arm [B]* is a comparison of ordinal shift in scores on mRS at 3 months. The mRS is a widely used instrument for grading the impact of stroke treatments, with scaling of: 0 = no symptoms at all; 1 = no significant disability despite symptoms, but able to carry out all usual duties and activities; 2 = slight disability, unable to carry out all previous activities but able to look after own affairs without assistance; 3 = moderate disability requiring some help, but able to walk without assistance; 4 = moderate-severe disability, unable to walk without assistance and unable to attend to own bodily needs without assistance; 5 = severe disability, bedridden incontinent, and requiring constant nursing care and attention; 6 = dead.

*Secondary outcomes are:* (a) symptomatic ICH based on NINDS criteria of brain imaging (or necropsy) confirmed ICH with  $\geq 1$  points deterioration in NIHSS score or death within 36 hours from baseline; (b) symptomatic ICH, defined by SITS-MOST criteria, as large ('type II') parenchymal ICH with  $\geq 4$  points decline in NIHSS score or death within 36 hours from baseline; and (c) ICH of any type in brain imaging  $\leq 7$  days of treatment; (d) good outcome, defined by scores 0-1 on the mRS (e) death or major disability, defined by scores 3-6 on the mRS, (e) death, (f) disability (mRS score 3-5), (g) neurological deterioration  $\geq 4$  points decline in NIHSS score over 72 hours, (h) HRQoL by the EuroQoL, (i) admission to residential care, and (j) health service use for calculation of resources and costs.

### RESULTS AND OUTCOME OF ARM [A]

In arm [A], the primary outcome occurred in 855 of 1607 participants (53.2%) in the low-dose group and in 817 of 1599 participants (51.1%) in the standard-dose group (OR 1.09; 95% CI 0.95 to 1.25; the upper boundary exceeded the noninferiority margin of 1.14;  $P = 0.51$  for noninferiority). Low-dose rtPA was noninferior in the ordinal analysis of mRS scores (unadjusted common OR 1.00; 95% CI 0.89 to 1.13;  $P = 0.04$  for noninferiority). Major sICH occurred in 1.0% of the participants in the low-dose group and in 2.1% of the participants in the standard-dose group ( $P = 0.01$ ); fatal events occurred within 7 days in 0.5% and 1.5%, respectively ( $P = 0.01$ ). Mortality at 90 days did not differ significantly between the two groups (8.5% and 10.3%, respectively;  $P = 0.07$ ). Conclusion: In patients with AIS low dose rtPA was not shown to be noninferiority of standard-dose rtPA with respect to death and disability at 90 days. However, there were significantly fewer sICH and deaths with low-dose rtPA.

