**Statistical considerations** A sample size of 3300 (1650 per group) estimated for arm [A] (i.e. rtPA dose) estimated to provide (i)  $>90\%$  power to detect non-inferiority (relative margin 14% [i.e. relative risk 1.14], absolute margin rate 6.5%) of low-dose rtPA on the primary outcome (one-sided  $\alpha = 0.025$ ) and (ii)  $\geq 80\%$  power to detect plausible 40% reductions in risks of sICH with low-dose rtPA (2-sided  $\alpha = 0.05$ ) with 5% drop-out was achieved. . Arm [A] completed recruitment in August 2015 with 3310 patients randomised. A sample size of 2100 (1050 per group) for arm [B] (i.e. BP lowering intensities) will provide  $\geq 80\%$  power to detect superiority of intensive BP lowering on the primary outcome and any ICH (2-sided  $\alpha = 0.10$ ) with 5% drop-out. Given overlap of 939 patients in the combined arms [A] and [B], an expected total of 4500 patients will participate in the study.

**Quality assurance and bias control** The study will be conducted at sites with established acute stroke units and thrombolysis programs. Regionally-based clinical research monitors will perform online, on-site data verification; and monitor conduct of the study, initially after the first few patients are randomised at a site and then at least once annually, according to patient recruitment numbers, whilst participating in the trial. As ENCHANTED is an open trial of differing management strategies in a critical illness, monitoring serves to confirm that investigators are adhering to the protocol and GCP Guidelines, and the accuracy of data. Monitoring by trained staff will confirm: (i) demographic and consent details of randomised patients; (ii) details of all SAEs against source documents; (iii) collect/correct outstanding/missing data; and (iv) check selected variables against source documents in a 10% random selection of patients.

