All randomised patients will be followed up to 90 days, or death if prior to 90 days. Patients who do not follow the protocol and/or discontinue allocated management should still be followed up to 90 days as their data will be analysed on the 'intention to treat' principle. **Table 5** illustrates the schedule and nature of the data collection required during the study period. The paper version of the case report forms (CRFs) will be supplied with the procedure manual, as a reference only, together with a guide to completion of each data element and a definition of terms.

All data entry will be completed on a password protected study website. This web-based data management system will allow for real time data query generation for values entered outside of pre-set valid ranges and consistency checking. This system will speed up data reporting and assist overall trial management for all participating centres. In addition to the web-based data entry, BP and drug usage will also be recorded on a paper CRF at the patient's bedside as part of the patient's usual medical record management.

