### 15. STATISTICAL CONSIDERATIONS

#### 15.1 Sample size

Arm [A] comparison of low- versus standard-dose rtPA Based on pooled trials data in the Cochrane review of thrombolysis in AIS, the rate of death or disability (mRS score of 2-6) in patients who receive standard-dose i.v. rtPA is 50%. Non-randomised studies suggest that low-dose rtPA provides similar clinical outcomes to the standard-dose rtPA (i.e. risk ratio 1.0). For comparison between low- and standard-dose rtPA, a non-inferiority margin is based on the pooled Cochrane review of thrombolysis in AIS, where the overall risk ratio of standard-dose rtPA versus control (placebo) with respect to death or disability was 0.76 (95%CI 0.66-0.87). Taking a conservative approach, as used in the Ongoing Telmisartan Alone and in Combination with Ramipril Global Endpoint Trial (ONTARGET), the 40th percentile point around the risk reduction estimate (0.77) rather than the observed risk ratio has been chosen as a more robust reference to describe the effects of standard-dose rtPA, which can be translated into a margin of excess risk of placebo versus standard-dose rtPA of 1.29. As recommended by the United States Food and Drug Administration (FDA), the clinical margin representing the largest acceptable inferiority of the test to control is set at 50% (i.e. risk ratio 1.14) of the margin of the excess risk of 1.29. Thus, a *relative non-inferiority margin* of 14% (i.e. risk ratio 1.14) provides assurance that low-dose rtPA retains at least half of the effects of standard-dose rtPA, provided the upper limit of the 95% CI of low- versus standard-dose rtPA is less than this non-inferiority margin. However, as there is potential for a negative interaction between intensive BP lowering and low-dose rtPA, the primary event rates will be 46.25% in patients who receive standard-dose rtPA and 46.75% in those who receive low-dose rtPA (**Table 6**), such that the *absolute non-inferiority margin rate* will be 6.5% (relative non-inferiority margin of 14% x the primary event rate in standard-dose rtPA group of 46.75%). A sample size of 3300 (1650 per group) provided >90% power (1-sided  $\alpha = 0.025$ ) to achieve the non-inferiority setting (assuming

a 5% drop-out) with the ability also to make an assessment of the superiority of low- versus standard-dose rtPA. Arm [A] recruitment completed with 3310 patients in August 2015.

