*In summary, a sample size of 3300 (1650 per group) for arm [A] (i.e. rtPA dose) provided >90% power to detect (i) non-inferiority (relative margin 14% [i.e. relative risk 1.14], absolute margin rate 6.5%) of low-dose rtPA on the primary outcome (one-sided  $\alpha = 0.025$ ), and (ii)  $\geq 80\%$  power to detect plausible 40% reductions in risks of sICH with low-dose rtPA, with 5% drop-out. Arm [A] recruitment completed with 3310 patients in August 2015. A sample size of 2100 (1050 per group) for arm [B] (i.e. BP lowering intensities) will provide  $\geq 80\%$  power to detect superiority of intensive BP lowering and any ICH (2-sided  $\alpha = 0.10$ ) with 5% drop-out. Given overlap of 939 patients in the combined arms [A] and [B], an expected total of 4500 patients will participate in the study.*

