### **17.6 Data Safety Monitoring Board (DSMB)**

*Responsibilities:* Monitor blinded response variables and serious adverse events for early dramatic benefits or potential harmful effects using the approach developed by Sir Richard Peto for safety monitoring and provide reports to the ICC on recommendations to continue or temporarily halt recruitment to the study.

Members of the DSMB include:

[name] (Chair), University of Sydney, Sydney, (NSW) Australia;

[name], University of Edinburgh, Edinburgh, Scotland;

[name], Royal Perth Hospital, Perth, (WA) Australia;

[name], Hôpital Lariboisière, Paris, France;

[name] [name], Prince of Wales Hospital, Chinese University of Hong Kong, Hong Kong.

A DSMB will review unblinded data from the study at regular intervals during follow-up, and will monitor BP separation (between the two groups), drop-out and event rates. Two interim efficacy analyses are planned after 30% and 60% of the patients have been followed up at 90 days. Prior to the first interim analysis a detailed Statistics Analysis Plan (SAP) will be completed and placed in the file. The SAP will contain a more comprehensive explanation than described herein of the methodology used in the statistical analyses, and in particular will specify the stopping rule used. The SAP will also contain the rules and data handling conventions used to perform the analyses, and the procedure used for accounting for missing data.

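### Arm A's non-inferiority margin is set and powered as a risk ratio of 1.14 (6.5 points absolute), but the verdict tests an odds ratio against 1.14, and the verdict depends on the scale

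*Protocol*

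**What the plan says.** The Summary Protocol (Statistical considerations) describes arm A as powered for "non-inferiority (relative margin 14% [i.e. relative risk 1.14], absolute margin rate 6.5%) of low-dose rtPA on the primary outcome". The closing summary of section 15.1 repeats it: "relative margin 14% [i.e. relative risk 1.14], absolute margin rate 6.5" per cent.

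Section 15.1 builds the margin on the risk ratio scale. It starts from a pooled risk ratio of 0.76 for standard-dose rtPA against control, takes the 40th percentile point (0.77), inverts that to an excess risk of 1.29, and halves the excess. Its claim for the resulting relative limit reads "of 14% (i.e. risk ratio 1.14) provides assurance that low-dose rtPA retains at least half of the effects of standard-dose rtPA". It then attaches a decision rule, which is a condition on the confidence interval: "provided the upper limit of the 95% CI of low- versus standard-dose rtPA is less than this non-inferiority margin". The planned event rates are 46.25% (standard dose) and 46.75% (low dose), with 1650 per group, one-sided alpha 0.025, 5% drop-out and power above 90%.

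The arm A results paragraph in section 9 gives 855/1607 events on low dose and 817/1599 on standard dose, then "OR 1.09; 95% CI 0.95 to 1.25; the upper boundary exceeded the noninferiority margin of 1.14", with P = 0.51 for non-inferiority. It concludes that non-inferiority was not shown. Protocol section 20 and the SAP introduction repeat that conclusion. The same results paragraph calls the ordinal mRS result non-inferior (common OR 1.00, 0.89 to 1.13, P = 0.04) and states no margin for it.

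**The concern.** An odds ratio and a risk ratio are close only when the event is rare. Here about half the patients have it, so 1.14 on one scale is a much stricter limit than 1.14 on the other. The documents give no odds ratio margin, no conversion and no reason for changing scale. Two things are at stake: whether the stated verdict follows from the stated rule, and whether the retention-of-effect argument and the power claim belong to the margin that was applied.

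**Working it through.** **1. Reproduce the reported odds ratio.** Inputs are the printed counts.
- OR = (855 × 782)/(752 × 817) = 1.088.
- SE(log OR) = √(1/855 + 1/752 + 1/817 + 1/782) = 0.0707, so the 95% CI is 0.947 to 1.250, as printed.
- Test against 1.14: z = (ln 1.088 − ln 1.14)/0.0707 gives one-sided P = 0.256 and two-sided P = 0.511. The printed 0.51 is the two-sided value. This confirms that 1.14 was applied as an odds ratio.

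**2. Same counts on the stated scales.** p(low) = 0.5320; p(standard) = 0.5109.

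| Measure | Estimate (95% CI) | SE | Margin | One-sided P | Upper limit inside? |
|---|---|---|---|---|---|
| Risk ratio | 1.041 (0.974 to 1.113) | 0.0339 (log) | 1.14 | 0.004 | Yes |
| Risk difference | 2.11 points (−1.35 to 5.57) | 1.76 points | 6.5 points | 0.006 | Yes |
| Odds ratio | 1.088 (0.947 to 1.250) | 0.0707 (log) | 1.14 | 0.256 | No |

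**3. Convert the margins.**
- RR 1.14 at the planned 46.25%: 1.14 × 0.4625 = 0.527, which is OR 1.30. At the observed 51.1% it is OR 1.34.
- OR 1.14 at either control rate adds about 3.3 points, or RR 1.07 (at 46.25%) to 1.06 (at 51.1%).

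**4. Planned power.** Evaluable n = 1650 × 0.95 = 1567.5 per group; rates 46.75% and 46.25%. Power = Φ[(margin − true effect)/SE − 1.96], with log scales for the ratios.
- Risk difference: (0.065 − 0.005)/0.01782 − 1.96 = 1.41, so 92%. The plan's >90% reproduces.
- Risk ratio: (0.1310 − 0.0108)/0.0383 − 1.96 = 1.18, so 88%.
- Odds ratio: (0.1310 − 0.0201)/0.0716 − 1.96 = −0.41, so 34% (45% if the true rates are equal).
- 90% power on OR 1.14 needs 6865 evaluable per group, or 2 × 6865/0.95 ≈ 14,450 randomised. With equal rates it needs 4924 per group, or about 10,400. The plan had 3300.

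**5. Unanalysed patients.** 3310 randomised − 3206 analysed = 104. The split by arm is not given. Assuming 1655 per arm, 48 low-dose and 56 standard-dose patients are missing.

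| Event rate among missing (low / standard) | Upper limit, RR | Upper limit, risk difference |
|---|---|---|
| 0% / 0% | 1.120 | 5.7 points |
| 51.1% / 51.1% | 1.110 | 5.5 points |
| 100% / 100% | 1.102 | 5.2 points |
| 68% / 34% | 1.134 | 6.5 points (limit reached) |
| 73% / 29% | 1.140 (limit reached) | 6.8 points |
| 100% / 0% | 1.180 | 8.6 points |

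With equal rates among the missing, both stated margins are still met. They fail only when those rates differ by about 34 points (absolute margin) or 44 points (risk ratio). Arm splits between 1640/1670 and 1670/1640 move the limits by at most 0.005 in RR and 0.1 point.

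**6. Ordinal result.** If its margin was also 1.14 (an assumption), the printed interval, allowing for rounding, gives one-sided P of 0.016 to 0.023 and two-sided P of 0.031 to 0.047. The printed 0.04 fits only a two-sided value.

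**The case against.** Arm A is closed and published, the current protocol version exists to run arm B, and the results paragraph is a recap. Arm B's endpoint, sample size and analysis do not use the verdict. That is correct and limits the consequences. The protocol and SAP nevertheless still assert the verdict, and the protocol sets it beside a margin from which it does not follow.

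Section 17.6 leaves to a SAP "the rules and data handling conventions used to perform the analyses, and the procedure used for accounting for missing data", and an arm A plan that is not supplied may have prespecified an odds ratio margin. This stands as a limit on what can be concluded. If so, the protocol's margin text, justification and power describe a different test.

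The odds ratio test is the stricter one, so no false claim of non-inferiority arose on the binary endpoint. That is also true, but a stricter unstated margin is still not the stated one.

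Section 15.1 ties the confidence limit rule to the relative margin. The 6.5 points are that margin times an assumed event rate (14% of the observed 51.1% would be 7.2 points). This is fair: the risk ratio is the cleaner reading, power on it is 88%, and the result meets it too.

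The 104 missing patients are 3.1% of those randomised, within the planned 5%, and are a side issue. They matter only because reversing a non-inferiority statement on complete cases calls for a check, particularly as section 10 says of patients who leave the protocol that "their data will be analysed on the 'intention to treat' principle".

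**Conclusion.** The concern holds. On the margin that the protocol states, justifies and powers, the printed counts meet the rule: upper limits 1.11 against 1.14, and 5.6 against 6.5 points. On the odds ratio scale actually used, the rule fails (1.25 against 1.14), and planned power on that scale was about 34% rather than above 90%. The stated margin and the stated verdict cannot both stand without further text.

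The estimates are unadjusted Wald calculations on 3206 of 3310 patients. The missing-data limits assume equal allocation. Which scale was prespecified cannot be settled from these documents. This must be fixed because a primary non-inferiority conclusion changes with the scale; it concerns the statistical criterion only.

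**What to change.** State the prespecified scale of the arm A margin and where it was prespecified. Then reconcile the Summary Protocol, the arm A results paragraph in section 9, section 15.1, section 20 and the SAP introduction.

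- **If the margin is the risk ratio or absolute margin as written:** report the risk ratio and risk difference against 1.14 and 6.5 points with one-sided P values. Add a sensitivity analysis for the 104 unanalysed patients, amend the non-inferiority statement to match, and keep the odds ratio as descriptive.
- **If an odds ratio margin of 1.14 was prespecified:** say so in the Summary Protocol and section 15.1, justify it on that scale, and restate power as about 34% (45% with equal rates).

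In both cases, label P = 0.51 as two-sided or replace it with the one-sided 0.26, and state the margin and sidedness used for the ordinal analysis.

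The cost is wording, re-tabulation from existing counts and, in the first case, one sensitivity table. No new data are needed. The sponsor must check the arm A analysis plan and align the text with the published report.
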